### Subgroups

From the base study population described above, 5 clinical subgroups will be defined based on the presence of psychiatric diagnoses during the 30 days prior to and inclusive of the treatment change under study (index date) and who have this same diagnostic code from more than one provider to increase the validity of the diagnostic groups. The subgroups will be defined by codes to capture 1) uncomplicated schizophrenia (with schizophrenia codes from at least 2 different providers and without any diagnoses that would qualify them for the other subgroups during the 365 days prior to the index date), 2) schizoaffective disorder (ICD-9: 295.7) as the most recent schizophrenia-spectrum diagnosis, 3) depressive (ICD-9: 293.83, 296.2, 296.3, 296.9, 298.0, 300.4, 311), 4) manic (296.0, 296.4-296.8), and 5) anxiety (293.84, 300.00-300.02, 300.09, 300.20-300.23, 300.29, 300.3, 300.7, 308.0-308.9, 309.21, 309.81, 312.39, 313.0, 313.21, 313.23). These subgroups are defined to reflect the reason for the change in treatment.

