### Comparators

Pharmacological treatment options for patients with schizophrenia who are nonresponsive to antipsychotic monotherapy will include (1) initiation of a second antipsychotic, (2) initiation of an antidepressant, (3) initiation of a mood stabilizer and (4) initiation of a benzodiazepine.

Within each clinical subgroup, treatment options may be refined by exclusions at the drug class or individual agent level. For example, antidepressants are generally not considered treatment alternatives in patients presenting with mania, but could reasonably be considered for patients in the remaining four schizophrenia subgroups: depression, anxiety, schizoaffective disorder, and uncomplicated schizophrenia. Unless it is not considered a reasonable treatment option for a specific subgroup, initiation of a new antipsychotic will serve as the reference category because it is a frequently recommended approach to improving treatment response and is a common treatment strategy across all of the clinical subgroups under study. A survey on the prescribing behaviors of clinicians who prescribe psychotropic medications for individuals with schizophrenia will inform these choices.

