#### AP treatment Initiation year

2002

2003

2004

2005

2006

2007

2008

2009

Diagnostic History, past year	ICD-9-CM Codes*
Depression	293.83, 296.2x, 296.3x, 296.9x, 298.0x, 300.4x, 311.xx
Anxiety	293.84, 300.0x, 300.2x, 300.3x, 308.3x, 309.21, 309.81, 313.0x, 313.2x, 313.89
Bipolar	296.xx (not 296.2x or 296.3x or 296.9x)
Substance use disorder	291.xx, 292.xx, 303.xx, 304.xx
Moderate/severe mental retardation	318.xx
HIV	042, 043, 044, 079.53, V08
Neoplasms	140.xx-239.xx (Exclude people with malignant neoplasms 140.xx-205.xx)
Diabetes	250.xx
Obesity	270.xx
Hyperlipidemia	272.0x-272.4x, 272.7x, 272.9x
White blood cell diseases	288.xx, 289.xx (exclude neutrophil d/o 288.00-288.04, 288.09, 288.1x)
Anemia	280.xx-285.xx
Drug-related dyskinesia	333.85
Hypertension	401.xx-405.xx
Ischemic heart disease	410.xx-414.xx
Pulmonary circulation diseases	415.xx-417.xx
Cardiac dysrhythmias	427.xx
Heart failure	428.xx
Cerebrovascular disease	430.xx-438.xx
Acute bronchitis and bronchiolitis	466.xx
Chronic bronchitis	491.xx
Pneumonia	480.xx-486.xx
Emphysema	492.xx
Asthma	493.xx
Appendicitis	540.xx-543.xx
Noninfectious enteritis and colitis	555.xx-558.xx
Diverticula of intestine	562.xx
Intestinal obstruction	560.xx
Chronic liver disease and cirrhosis	571.xx
Acute & chronic pancreatitis	577.0x, 577.1x
Cholelithiasis	574.xx
Acute kidney failure	584.xx
Chronic kidney failure	585.xx

Kidney infections	590.xx
Cellulitis and abscess	681.xx–682.xx
Osteoarthritis and allied disorders	715.xx
Intervertebral disc disorder	722.xx
Fractures, all sites	800.xx–829.xx
Fracture of neck of femur	820.xx
Poisoning by psychotropic medication	969.xx
Poisonings	960.xx–989.xx
Suicide and self-inflicted injury	E950-959
Intracranial injury	815.xx-854.xx
Severe cardiovascular diseases	401.0x-404.9x, 410.xx-416.xx, 425.xx-437.xx, 440.xx-447.xx
Schizophreniform	295.4x
Schizoaffective	295.7x

---

\* x indicates inclusion of any 5th digit if available for a diagnosis code.

xx indicates inclusion of any 4th and 5th digits if available for a diagnosis code.

Medication history, past year	Drug class
Psychotropic medication	
Antidepressants	SSRI/SNRI/mirtazapine, TCA and heterocyclic compounds, MAOI, trazodone-related antidepressants, bupropion
Mood Stabilizer	lithium, primary anticonvulsant, secondary anticonvulsant
ADHD medication	psychostimulants, alpha-agonists
Anxiolytic/hypnotics	benzodiazepines, GABA agonists, other newer or older anxiolytic/hypnotic

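### Episodes that meet the manic definition are kept out of the antidepressant comparison in one subgroup but can enter it in another, and code 296.1 can fall into uncomplicated schizophrenia

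*Combined protocol and SAP*

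**What the plan says.** The Subgroups section assigns patients "based on the presence of psychiatric diagnoses during the 30 days prior to and inclusive of the treatment change under study (index date"), and asks for the same diagnostic code from more than one provider. The depressive entry reads "depressive (ICD-9: 293.83, 296.2, 296.3, 296.9, 298.0, 300.4, 311") and the manic entry "manic (296.0, 296.4-296.8"). Schizoaffective disorder needs 295.7 "as the most recent schizophrenia-spectrum diagnosis". Only uncomplicated schizophrenia carries an exclusion: "without any diagnoses that would qualify them for the other subgroups during the 365 days prior to the index date". The section gives the purpose of the grouping: "These subgroups are defined to reflect the reason for the change in treatment".

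The Comparators section says that "antidepressants are generally not considered treatment alternatives in patients presenting with mania" and accepts them in the other four subgroups. Table 5 (Sample size) accordingly shows NA for antidepressants under Mania only. Refinement of the options is described by drug class or agent within a subgroup, not by a patient's other diagnoses.

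Appendix 2, in the past-year diagnostic history, defines the propensity-score variable Bipolar as "296.xx (not 296.2x or 296.3x or 296.9x").

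**The concern.** The Comparators section reads as if each episode had one subgroup, but the Subgroups section does not make that so. An episode with qualifying manic and depressive codes belongs to both groups. In one, antidepressants are set aside as not generally an alternative. In the other, the same episode counts in a contrast against antidepressants.

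Two things are at stake. Aim 1 rests on comparing treatments that are options for the patients compared, in groups that share a reason for the change, and overlap blurs both. Also, current manic symptoms may plausibly influence both the drug chosen and psychiatric admission, the primary outcome. The planned covariates do not isolate them, so a difference between arms could go unadjusted and would not appear in the balance check.

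The 296.1 gap works in the other direction: a patient whom the plan's own appendix counts as bipolar can sit in the group meant to be free of such diagnoses.

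**Working it through.** **1. Rules side by side.** The sections on cohort identification, subgroups, comparators, analysis and sensitivity analyses, and Appendix 1, were read for any hierarchy, tie-break or exclusivity rule.

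| Subgroup | Entry | Excludes manic codes? | Antidepressant episodes, Table 5 |
|---|---|---|---|
| Uncomplicated | 295 codes, at least 2 providers | Yes, 365 days | 25,061 |
| Schizoaffective | 295.7 most recent | No | 9,692 |
| Depressive | listed codes, 30 days | No | 4,646 |
| Anxiety | listed codes, 30 days | No | 1,110 |
| Manic | 296.0, 296.4-296.8, 30 days | – | NA |

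The three unguarded groups hold 9,692 + 4,646 + 1,110 = 15,448 antidepressant episodes. This is the pool in which overlap can occur, possibly counting an episode more than once. It is not the number affected.

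**2. Code lists.** Within 296.0 to 296.9, the depressive list takes 296.2, 296.3 and 296.9, and the manic list takes 296.0 and 296.4 to 296.8. Only 296.1 is left over. Appendix 2's Bipolar variable is all of 296 less 296.2, 296.3 and 296.9, so it includes 296.1. The two lists differ by exactly that code.

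**3. What the covariates can see.** Any episode with a current manic-list code has Bipolar = 1, but so does one whose last such code was ten months earlier. Past-year mood-stabilizer use helps less than it seems to: stable monotherapy requires no other psychotropic for at least 90 days before the index drug, so that variable reflects use before that window. Bias can remain if, among those with Bipolar = 1, the share with current codes differs between arms.

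**4. Illustration of size, unadjusted.** Assume current manic codes in a share p1 = 0.05 of the antidepressant arm and p0 of a comparator arm, raising the admission hazard by HR. None of these values is in the documents. Factor on the comparator/antidepressant ratio = [1 + p0(HR − 1)] / [1 + p1(HR − 1)].

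| p0 | HR 1.3 | HR 1.5 | HR 2 |
|---|---|---|---|
| 0.25 | 1.075/1.015 = 1.06 | 1.125/1.025 = 1.10 | 1.25/1.05 = 1.19 |
| 0.15 | 1.045/1.015 = 1.03 | 1.075/1.025 = 1.05 | 1.15/1.05 = 1.10 |

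**5. Cost in precision.** The plan states 5.0 points with at least 80% power at 1,534 patients per group in the depression subgroup (70% of 2,192). It gives no base rate. Power is 80.0% for 40% versus 45%, and 79.1% with rates centred on 50%, so the figure reproduces closely. With rates centred on 50%, detectable difference ≈ (1.960 + 0.842) × √(0.5/n):

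- n = 1,534: 5.06 points.
- 5% removed, n = 1,457: 5.2 points.
- 10% removed, n = 1,381: 5.3 points.
- 30% removed, n = 1,074: 6.0 points.

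For the smallest anxiety arm (70% of 611, or 428), 10% removal leaves 385 and moves the difference from 9.6 to 10.1 points.

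**The case against.** Overlapping subgroups, analysed separately, are a legitimate design. Dual membership also needs each diagnosis confirmed by more than one provider within 30 days, which may make it uncommon. The main analysis is propensity-weighted. It includes past-year bipolar codes, mood-stabilizer use, psychiatric admissions and emergency contacts, and it plans balance checks, boosted models and a sensitivity analysis for unmeasured confounding. All of this stands, and it is why no residual bias can be claimed as shown.

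A reader might infer that mania-coded patients have almost no chance of an antidepressant and would get extreme weights. The documents give no such frequency, and the illustration itself does not imply it. In the depression column, 5% of 4,646 is 232 antidepressant episodes and 25% of 2,192 is 548 second-antipsychotic episodes. The antidepressant probability is 232/780 = 0.30, a weight of about 3.4. Against mood stabilizers (25% of 1,296 = 324) it is 232/556 = 0.42, a weight of about 2.4.

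A reader might also take every manic-list code as presenting mania. Appendix 2 gives nearly the same range the label Bipolar, so that is not established. For schizoaffective disorder the objection is stronger still: the Goal section makes persistent mood symptoms part of the diagnosis, and the Comparators section accepts antidepressants there.

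What the objection does not answer is that the Subgroups and Comparators sections treat the same episode in two ways, or that 296.1 is in no subgroup list.

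**Conclusion.** The point holds as a gap in the cohort rules. Episodes meeting the full manic definition are kept out of the antidepressant contrast in one subgroup and can enter it in up to three others, and no planned covariate separates current from earlier manic codes. The omission of 296.1 is a plain mismatch between two code lists.

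The size is unknown. Overlap counts are not reported, and the bias left after weighting cannot be computed from the documents. The 1.03 to 1.19 range describes crude ratios under assumed prevalences and hazard ratios. It should not be read as the error expected in the reported results. The case for change rests on the inconsistency and on how cheaply it can be removed before the cohort is fixed.

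**What to change.** 1. Add 296.1 to the manic list in the Subgroups section, so that it also counts in the uncomplicated exclusion.
2. Reconcile the Subgroups and Comparators sections: assign episodes that meet the full manic definition, including the two-provider rule, to the manic subgroup only and not also to the depressive or anxiety subgroups. Report the overlap counts. The rule should use the full definition, because removing every episode with any manic code could drop single-provider codes from every subgroup. The Sensitivity Analyses section lists the two-provider requirement as a separate analysis, so its status in the main definition should be confirmed.
3. In the depressive, anxiety and schizoaffective subgroups, add a 30-day manic-code indicator to the propensity score and balance check. In the schizoaffective subgroup, add a sensitivity analysis that drops episodes with concurrent manic codes from all arms, so that the reference group stays the same across contrasts.

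The cost is eligibility wording, cohort code, and some loss of depressive and anxiety episodes, with the precision loss shown above. Reassigned antidepressant starters would leave the depressive and anxiety contrasts without entering a manic one, so their number should be reported. Which drugs are real options for patients with concurrent codes remains for the sponsor to settle.

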### Sensitivity Analyses

We will conduct sensitivity analyses to confirm findings from the primary analyses and to examine their generalizability. In addition to the primary 360-day intention-to-treat analyses we will conduct 180-day intention-to-treat analyses and as-treated analyses. Another sensitivity analysis will examine subgroups of people with depression, anxiety, or mania diagnoses that are listed by more than one provider.

**Quantitative Sensitivity Analyses for Unmeasured Confounders.** Because the observed relative risk is a closed-form function of the balance of confounders among exposure groups, the strength of the confounder, and the prevalence of the confounder, it is possible to estimate the extent of unmeasured and thus unadjusted confounding necessary to fully explain the observed findings, i.e., would move the observed relative risk to statistical insignificance (the null).

To quantify how strong unmeasured confounding would have to be to explain the observed effect sizes among our comparison groups, we will use the array approach to understand how the strength of unmeasured confounders with known associations with our outcomes, such as BMI and risk of diabetes, and the confounder imbalance among study groups might affect the observed relative risk.

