### Sample size

Table 5 presents sample size estimates for national 2001-2010 Medicaid data based on our preliminary analyses. For example, we expect that the following treatments with corresponding numbers will be options for the depression symptom subgroup: second antipsychotic (n = 2,192), mood stabilizer (n = 1,296), antidepressant (n = 4,646), and benzodiazepine (n = 1,199). We will then, for example, compare 2,192 patient episodes with a second antipsychotic to 2,192 propensity-score matched patient episodes that were treated with an antidepressant. The 1:1 matching method uses a nearest neighbor algorithm. As recommended for observational studies, we will use a caliper width of 0.2 of the standard deviation of the logit of the propensity score to ensure appropriate matching.

Our power analysis is based on two-sided ( $\alpha = .05$ ) tests for differences in proportions between treatment groups, which depend upon the sample size of each group and the probability of the outcome. To demonstrate power, we conservatively use the expected number of distinct patients rather than episodes (distinct patients equal approximately 70% of the episodes in Table 5). Final statistical analyses of individual episodes will have greater power (i.e., be able to detect even smaller percent differences) and will incorporate random effects to account for patients who contribute more than one episode.

Table 5: Estimated sample sizes of selected schizophrenia treatment episodes (2001-2010)

	Uncomplicated Schizophrenia	Schizoaffective Disorder	Depression	Mania	Anxiety
Second Antipsychotic	27,005	6,393	2,192	1,580	611
Mood Stabilizer	9,954	4,734	1,296	2,107	NA
Antidepressant	25,061	9,692	4,646	NA	1,110
Benzodiazepine	12,248	3,681	1,199	840	1,099

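### The manic subgroup is defined by codes that Appendix 2 labels bipolar, without regard to episode polarity, so its results cannot be read as evidence on mania alone

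*Combined protocol and SAP*

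**What the plan says.** The Subgroups section assigns patients by diagnoses recorded "during the 30 days prior to and inclusive of the treatment change under study (index date", with the same code from more than one provider. The two lists that matter here are "4) manic (296.0, 296.4-296.8" and "3) depressive (ICD-9: 293.83, 296.2, 296.3, 296.9, 298.0, 300.4, 311". Of the purpose, the section says: "These subgroups are defined to reflect the reason for the change in treatment".

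In the Appendix 2 propensity score list, the Bipolar covariate is defined as "296.xx (not 296.2x or 296.3x or 296.9x". The Depression covariate there takes the same three 296 categories as the depressive subgroup: 296.2, 296.3 and 296.9.

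The Comparators section reasons that "antidepressants are generally not considered treatment alternatives in patients presenting with mania", and Table 5 shows NA for antidepressants under mania. The Sensitivity Analyses section adds: "Another sensitivity analysis will examine subgroups of people with depression, anxiety, or mania diagnoses that are listed by more than one provider".

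**The concern.** The plan gives nearly the same codes two names, a manic presentation in one place and a bipolar diagnosis in another. Three things rest on the first name.

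- **Interpretation.** The Background poses a physician's question about manic symptoms, and the design overview makes the clinical subgroups the focus of the primary analyses. If the list admits depressed and unspecified episodes, a hazard ratio reported for mania describes a mixed group.
- **Comparators.** The antidepressant arm is left out because patients present with mania, yet the rule applies to everyone in the code range.
- **Confounding.** The Approach to confounding section relies on diagnostic subgroups to limit confounding by indication. If polarity varies within the subgroup and plausibly affects both drug choice and hospitalization, restriction has not done that work, and adjustment would have to.

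**Working it through.** **1. Compare the code lists (documents only).**

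- Appendix 2 Bipolar, all of 296 less .2, .3 and .9: {296.0, 296.1, 296.4, 296.5, 296.6, 296.7, 296.8}
- Manic subgroup: {296.0, 296.4, 296.5, 296.6, 296.7, 296.8}
- Difference: {296.1}
- Overlap of the manic list with the depressive list: none

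So 296.5 leads to the manic subgroup and not to the depressive one. Code 296.1 is on no mood subgroup list, and therefore does not by itself exclude a patient from uncomplicated schizophrenia.

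**2. What the codes mean.** The documents do not print the meanings; these are from ICD-9-CM. 296.5 is bipolar with most recent episode depressed, 296.6 mixed, 296.7 most recent episode unspecified, 296.8 other or unspecified, and 296.1 recurrent mania. The list thus admits a depressed-episode code and omits a manic one.

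**3. Can the planned adjustment separate polarity?** The subgroup code falls in the 30 days up to and including the index date; covariates come from the 365 days before initiation. Bipolar is therefore present for essentially every subgroup member (the only possible exceptions are patients whose qualifying claims all fall on the index date). A constant covariate adjusts for nothing. Depression omits 296.5. No listed diagnosis covariate distinguishes 296.4 from 296.5.

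**4. Does any planned analysis vary polarity?** No. The extra sensitivity analysis on these subgroups concerns the number of providers.

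**5. Size.** From Table 5 ("Estimated sample sizes of selected schizophrenia treatment episodes (2001-2010"): 1,580 + 2,107 + 840 = 4,527 mania episodes. The share entering through 296.5, 296.7 or 296.8 is not given. Under assumed shares f:

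| f (assumed) | Episodes, 4,527 × f | Apparent gap if true gap is 10 points in manic patients and 0 in the rest, 10(1 − f) | Same, if −10 in the rest, 10(1 − f) − 10f |
|---|---|---|---|
| 10% | 453 | 9.0 | 8.0 |
| 25% | 1,132 | 7.5 | 5.0 |
| 50% | 2,264 | 5.0 | 0.0 |

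These are illustrations of averaging only. They ignore confounding by polarity, which could push an estimate either way.

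**6. Price of restricting to manic or mixed codes.** Smallest detectable difference, two-sided α = 0.05, 80% power, 1:1, rates near 50%: d = (1.960 + 0.842) × √(0.5/n). As a check, the plan's n = 839 gives 2.802 × √(0.5/839) = 6.8 points, the figure stated in the Sample size section. The smallest mania arm is benzodiazepine: 840 × 0.70 = 588 patients.

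| Removed (assumed) | n | d |
|---|---|---|
| 0% | 588 | 8.2 points |
| 10% | 529 | 8.6 points |
| 25% | 441 | 9.4 points |
| 50% | 294 | 11.6 points |

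Adding patients coded 296.1 would offset some of this loss.

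**The case against.** The best defence is that the diagnosis must be recent and confirmed by more than one provider, that broad code groups are a normal compromise in claims data, and that many unspecified episodes may in fact be manic. All of that is fair, but neither the window nor the provider rule says anything about polarity. It is also true that the code meanings come from ICD-9-CM and not from the protocol's text; the conflict between the two labels needs no outside source.

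Propensity weighting gives partial help. Co-recorded depressive codes, past-year medication and prior admissions may act as proxies for polarity. None of them records it.

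Several stronger readings are tempting and are not supported:

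- *The subgroup takes all bipolar codes.* It omits 296.1.
- *It captures lifetime bipolar disorder.* The 30-day window rules that out.
- *Patients coded 296.5 who start an antidepressant are lost to the study.* They have no arm in this subgroup and do not enter the depressive one through that code. But the plan does not make the four subgroups other than uncomplicated schizophrenia mutually exclusive, so another qualifying code can place them elsewhere.
- *Leaving out antidepressant starters biases the remaining comparisons.* By itself it changes the target population; the documents show no further bias.
- *The result is diluted by a known amount.* Every input to such a figure is assumed.

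**Conclusion.** The concern holds as a mismatch between label and code list that carries through to the comparators and the adjustment. As written, the plan would report a bipolar group of mixed polarity as evidence on mania, with no diagnosis covariate and no planned sensitivity analysis that addresses polarity.

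It affects one of the five subgroups, 4,527 episodes in Table 5. How many are not manic, and how far and in which direction the estimates would move, cannot be determined from the documents. The conclusion rests on the two code lists in the plan and on the standard ICD-9-CM meanings. It does not depend on the assumed shares. It should be corrected before the analysis is run.

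**What to change.** 1. Label the broad group bipolar, as Appendix 2 does. Adding 296.1 makes the two lists identical and lets the restricted set sit inside the broad one.
2. Tabulate the group by 296.x code and treatment arm before any outcome analysis.
3. Base any conclusion about manic symptoms on the same weighted Cox analysis restricted to manic or mixed episode codes: 296.0, 296.1, 296.4 and 296.6.
4. In the broad-group analysis, add episode polarity (296.5 versus the other codes) to the propensity score.
5. Reconcile the mania rationale in the Comparators section with the codes actually used. Which treatments are compared in which group is for the sponsor to decide.

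Whether 296.5 should also move to the depressive list is left to the sponsor. The move would pool bipolar depression with the existing depressive codes and depart from Appendix 2, which does not count 296.5 as Depression.

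The data are existing claims, so the cost is code-list and label edits, re-tabulated Table 5 counts, one additional analysis, and the wider intervals shown in step 6 of the working.

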### Data source and cohort identification

The data source will be national (45-state) Medicaid Analytic Extracts data (2001-2010). The cohort will consist of adults who are 18 to 64 years old and diagnosed with schizophrenia who initiate a new psychotropic medication after a period of stable antipsychotic treatment. Individuals who are 65 or older because will be excluded because they also have Medicare and receive pharmacy benefits through Medicare Part D.

Schizophrenia will be defined as  $\geq 2$  outpatient claims or  $\geq 1$  inpatient claim for schizophrenia [ICD-9-CM: 295] during 365 days of consecutive Medicaid enrollment immediately prior to the index date. Stable antipsychotic monotherapy will be defined by filled prescriptions for only one second-generation antipsychotic (excluding clozapine), and no other psychotropics, for  $\geq 90$  days immediately preceding the start of the index medication (t0). After the  $\geq 90$  days of stable treatment with a single second-generation antipsychotic, study patients will have had a change in therapy defined as (1) addition of a second antipsychotic or (2) addition of a different psychotropic drug class (antidepressant, mood stabilizer, or benzodiazepine). To ensure the patients are in active treatment there must be an active supply of antipsychotic medication on t0.

The eligibility criteria select a cohort of individuals that are likely to have schizophrenia, have received antipsychotic monotherapy prior to the index date, and are still experiencing problems for which a new psychotropic medication strategy was initiated. A 1-year period of eligibility prior to follow-up initiation ensures sufficient time to collect service use related covariates to characterize cohort members.

Patients with stable clozapine monotherapy will be excluded because clozapine is largely reserved for the most severely ill patients. Patients who implement more than one change in therapy at the index date (e.g., addition of a mood stabilizer and an antidepressant) will also be excluded.

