## Approach to confounding

Physicians make treatment choices in light of available clinical information and as a result there is a risk of confounding by clinical indication for the treatments under study. Our design minimizes confounding by indication by focusing on diagnostic subgroups. To further reduce confounding, we will control for a broad range of potentially relevant factors from claims histories. These factors will be identified in the 365-day period before drug initiation and used to calculate propensity scores. In addition we will conduct sensitivity analyses to estimate the extent of unmeasured confounding necessary to fully explain our observed findings and we will conduct instrumental variable analyses if a suitable instrument is identified.

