Other psychiatric medication	modafinil, oxybate, phendimetrazine, benzphetamine
OB/GYN medication	oral contraceptives, other contraception, medroxyprogesterone
Metabolic and related medication	lipid-lowering drugs, hypothyroid treatment, antithyroid agents, anorexiant
Cardiovascular medication	thiazide diuretic, ACE inhibitor/ARBs, other anti-hypertensives, other cardiovascular drugs
Respiratory/allergy medication	non-sedating antihistamines, other antihistamines, Corticosteroids, other Asthma medications, Smoking cessation
Gastrointestinal medication	histamine 2 receptor antagonists, proton-pump inhibitors, other prescription dyspepsia, Antacids, anti H pylori, phenothiazine antiemetics, Ulcerative colitis treatment
Neurologic/musculoskeletal medication	migraine treatment/prevention, NSAID, includes coxibs, narcotic analgesic, Non-narcotic analgesic (acetaminophen), Cyclobenzaprine, other skeletal muscle relaxants, other rheumatologic
Antibiotics	
Diabetic medication	
Hyperlipidemia medication	
Severe cardiovascular medication	

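### In the uncomplicated subgroup, control of confounding by indication rests mainly on a propensity score with only thin markers of extrapyramidal effects and sleep disturbance

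*Combined protocol and SAP*

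**What the plan says.** The Subgroups section forms the groups as follows: "5 clinical subgroups will be defined based on the presence of psychiatric diagnoses during the 30 days prior to and inclusive of the treatment change". The codes cover schizoaffective, depressive, manic and anxiety diagnoses. The uncomplicated group needs schizophrenia codes from at least two providers and, over the prior year, none of the diagnoses that lead into the other four. The section then states: "These subgroups are defined to reflect the reason for the change in treatment".

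Approach to confounding relies on this: "Our design minimizes confounding by indication by focusing on diagnostic subgroups". It adds propensity scores built from the 365 days before initiation, a sensitivity analysis for unmeasured confounding, and an instrumental variable analysis if a suitable instrument is found.

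Appendix 2 lists the variables in the score. On the two conditions at issue:

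- **Movement side effects:** one diagnosis row, "Drug-related dyskinesia" (333.85).
- **Drugs for movement side effects:** no row. The neurologic/musculoskeletal row ends with "Cyclobenzaprine, other skeletal muscle relaxants, other rheumatologic" and names no antiparkinsonian or anticholinergic class.
- **Sleep:** no diagnosis row. The nearest item is the past-year drug row "benzodiazepines, GABA agonists, other newer or older anxiolytic/hypnotic".

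Data source and cohort identification requires, for at least 90 days before the index date, fills for "only one second-generation antipsychotic (excluding clozapine), and no other psychotropics".

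**The concern.** A subgroup defined by a recent depressive or anxiety code says something specific about why a drug was added. A subgroup defined by the absence of such codes says much less, and this is where most of the planned data lie. In that subgroup the propensity score has to do most of the work.

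Every cohort member is taking an antipsychotic at the index date, and the usual reference arm adds a second one. How well the current drug is tolerated is therefore a plausible influence on whether the prescriber adds another antipsychotic or something else. Sleep disturbance is a plausible influence on whether a benzodiazepine is chosen. If either also predicts psychiatric admission, the arms would differ on the primary outcome without any drug effect. The balance check under Propensity score estimation and application cannot show an imbalance in a variable that was never constructed.

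**Working it through.** The plan states no figure for this bias, so there is none to reproduce. The check has three parts.

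**1. Where the episodes lie (Table 5, Sample size).** Column sums:

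- Uncomplicated: 27,005 + 9,954 + 25,061 + 12,248 = 74,268
- Schizoaffective: 6,393 + 4,734 + 9,692 + 3,681 = 24,500
- Depression: 2,192 + 1,296 + 4,646 + 1,199 = 9,333
- Mania: 1,580 + 2,107 + 840 = 4,527
- Anxiety: 611 + 1,110 + 1,099 = 2,820

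The total is 115,448, and 74,268 / 115,448 = 64.3%. By treatment, the uncomplicated subgroup holds 12,248 of 19,067 benzodiazepine starts (64.2%) and 25,061 of 40,509 antidepressant starts (61.9%). The other four columns may overlap with one another. If they do, the number of distinct episodes is smaller and these shares are lower bounds. Table 5 holds planning estimates, not final counts.

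**2. What the existing proxies can see.** The look-back is 365 days. Past-year benzodiazepine fills cannot fall in the final 90 days, because benzodiazepines are one of the named psychotropic classes. That leaves 365 − 90 = 275 days at most. For other hypnotics the text is unclear. Appendix 2 lists them under psychotropic medication, which would exclude them from the final 90 days. The as-treated rule in Follow-up and censoring names only antipsychotics, mood stabilizers, antidepressants and benzodiazepines as psychotropic agents, which would let them run up to the index date. Antiparkinsonian drugs are in neither list, so fills close to the index date should be observable if the variable is built.

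**3. Illustrative size.** The array approach named under Sensitivity Analyses rests on the relation

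bias factor = [p1(RR − 1) + 1] / [p0(RR − 1) + 1],

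where p1 and p0 are the prevalences of the omitted marker in the two arms and RR is its relative risk for admission. The documents give none of these, so all are assumptions:

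| p1 vs p0 | RR | Calculation | Bias factor |
|---|---|---|---|
| 10% vs 5% | 1.25 | 1.025 / 1.0125 | 1.01 |
| 10% vs 5% | 2.0 | 1.10 / 1.05 | 1.05 |
| 30% vs 10% | 1.25 | 1.075 / 1.025 | 1.05 |
| 30% vs 10% | 1.5 | 1.15 / 1.05 | 1.10 |
| 30% vs 10% | 2.0 | 1.30 / 1.10 | 1.18 |

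For scale, take benzodiazepine against second antipsychotic in the uncomplicated subgroup. At the plan's 70% of episodes there are 0.7 × 12,248 ≈ 8,574 and 0.7 × 27,005 ≈ 18,904 patients. With an assumed 25% admitted in a year, there are about 6,869 events, and the benzodiazepine share is 0.312. The standard error of the log hazard ratio is 1/√(6,869 × 0.312 × 0.688) ≈ 0.026. It would be about 0.041 if 10% were admitted and 0.018 if 50% were. At 0.026, the smallest bias above is ln(1.0123)/0.026 ≈ 0.5 standard errors and the largest is ln(1.182)/0.026 ≈ 6.4. Both are overstated to the extent that weighting raises the standard error, and to the extent that covariates already in the score absorb part of the imbalance.

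**The case against.** The strongest reply has four parts.

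- **The causal premise is not in the documents.** A reader might infer that extrapyramidal effects and sleep disturbance are established reasons for choosing a benzodiazepine, so that this comparison is biased in a known direction. Nothing in the plan says so. This part of the objection stands, and neither direction nor size can be derived from the text.
- **The score is not empty on these conditions.** A reader might infer that both are wholly missing from it. They are not: 333.85 and past-year anxiolytic/hypnotic use are there. This also stands, but one code and a drug history that may stop 90 days early are partial cover.
- **The plan already has backstops.** The array analysis and the conditional instrumental variable analysis are planned, and Approach to confounding already presents the propensity score as a second layer of control. That is true, but the array analysis asks how strong an unmeasured factor would have to be. It does not replace adjusting for one that can be measured, and no instrument may be found.
- **Any covariate list can be lengthened.** The plan leaves selection to expert opinion. That is fair in general. Here, though, the candidates relate to the tolerability of the drug that every patient is taking, while Appendix 2 finds room for appendicitis and intestinal diverticula.

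A reader might also infer that, with samples this large, any such bias would be declared significant. The figures do not support that. At 0.5 standard errors a two-sided 5% test would reject a true null about 8% of the time.

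**Conclusion.** The point holds as a gap in the covariate list and as a limit on what the subgroups can achieve. It is not a demonstrated bias. From the documents alone, about 64% of planned episodes lie in a subgroup whose definition gives at most a coarse reason for the change, and the score that must compensate has thin markers of two plausible determinants.

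The possible size, a spurious relative risk of about 1.01 to 1.18, rests entirely on assumed prevalences and relative risks. It treats the marker as unrelated to the other covariates, so it probably overstates what would remain after adjustment. The low end could not be told apart from sampling error; the high end could. No stated sample size or power figure is affected. This is an inexpensive improvement that should be made before analysis, not a flaw that invalidates the design.

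**What to change.** Add to Appendix 2, and to the table of standardized differences, or justify leaving out:

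1. Antiparkinsonian/anticholinergic fills, as two variables: any in the past year, and any in the 90 days before the index date.
2. Drug-induced movement-disorder diagnoses beyond 333.85.
3. Sleep-disturbance diagnoses.

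Confirm the codes against the code set in force for each data year. State whether non-benzodiazepine hypnotics count as psychotropics under the 90-day rule, so that the reach of the existing hypnotic variable is clear.

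In Approach to confounding, add that the definition of the uncomplicated subgroup does not by itself identify a specific reason for the change, so control there rests mainly on the propensity score. Keep the array and instrumental variable analyses for what remains unmeasured.

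The cost is a few more covariates from claims already held and some added text. No new data are needed and no sample size changes.
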